6.6.5. Data Safety Monitoring Board

An independent Data Safety Monitoring Board (DSMB) composed of 3 liver experts will review the safety of patients enrolled in the trial. The DSMB will perform a safety data review every 3 months, the first review occurring 3 months after first patient randomized. A DSMB charter will define the role, responsibilities, rules, and tasks of the DSMB.

The DSMB will ensure that the patient and trial discontinuation rules are respected and will determine the causality assessment of the events described in sections 6.6.1, 6.6.2., and 6.6.3., in order to make the recommendation for trial /patient discontinuation. If the events are deemed unrelated to the study drug by the DSMB, then the patient or the trial will continue.

6.8. Description of Assessments

6.8.1. Histological Assessments

All possible attempts should be made to acquire a liver biopsy specimen of at least 2.0 cm in length, from a 16 gauge needle to ensure accurate staging of fibrosis and other histological lesions. A historical biopsy within 6 months of the Screening visit may be accepted as the Screening biopsy. The liver biopsy sample must be deemed adequate for evaluation by the pathologist for inclusion. Liver biopsies will be assessed by a local reader. This assessment will include an assessment of the adequacy of the specimen as well as the fibrosis stage and a determination that the biopsy is consistent with NASH. If either the historical or screening liver biopsy is deemed unacceptable, it may be repeated.

6.8.2. Assessment of newly synthesized proteins

Kinetic biomarkers will be analyzed to evaluate the pharmacodynamic effect of NTZ on fibrogenesis. Blood samples analyses will be performed after deuterated water intake before and after 24 weeks of treatment. The assessment will involve the analysis of the change (absolute and relative) from baseline between the post-dose and pre-dose deuterated water loading periods.

6.8.3. Biological Assessments (Table 2)

Chemistry:

HbA1c, fasting plasma glucose, insulin, HOMA-IR, fructosamine, alkaline phosphatase, ALT, AST, GGT, CPK, total and conjugated bilirubin, ferritin, creatinine, eGFR, uric acid, BUN, total cholesterol, HDL-C, LDL-C, triglycerides, albumin, lipase, amylase, electrolytes (sodium, potassium, chloride, calcium), MELD

Hematology:

Hematocrit (Hct), hemoglobin (Hb), platelet count, red blood cell count (RBC), white blood cell count (WBC) with differential (absolute and percentage) including lymphocytes, monocytes,

neutrophils, eosinophils, and basophils and, reticulocyte count and mean corpuscular volume (MCV).

Inflammatory markers:

hsCRP, fibrinogen, haptoglobin, resistin, TNF- α , TGF- β , IL-6, PAI-1

Coagulation Panel:

Prothrombin time (PT), and international normalized ratio (INR)

Pregnancy Tests:

Urine β -hCG (if positive, requires immediate confirmation with Serum β -hCG)

Urinary Tests:

Urinary dipstick analysis, urinary albumin, urinary creatinine, urinary ACR

Additional Tests:

Serology (HIV-1, HBsAg, HCVAb & HCV RNA (as needed)), serum cystatin C, troponin T, NT proBNP

Fibrosis Biomarker tests:

ELFTM test score, PIIINP, Hyaluronic acid, CK18, TIMP-1, YKL-40, Alpha 2 macroglobulin, miRNA, FGF19, FGF21, ProC3 and ProC6.

A laboratory manual will be provided

The manual will outline the collection and processing requirements for the laboratory. Blood sampling will be performed by trained personnel. Blood samples will be processed and shipped as outlined in the laboratory manual. Refer to the laboratory manual for exact amounts of blood required for each test.

The option to retest during the study is left to the Investigator's judgment.

Additional serum and plasma samples will be maintained for future analysis

Table 2 Biological assessments

Visit	Screening period				Treatment period											
	SV	S V2	SV3	S V 4	V 1	V 2	V 3	V4	V5	V6	V7	V8	V9	V10	EOS	ET
Day	-42	-14	-11	-7	1	29	57	85	113	141	155	158	162	169	+28 days	
Week	-6	-2			0	4	8	12	16	20	22			24	28	
Labs - Haematology haemoglobin, haematocrit, RBC, WBC, differential count, platelet count, reticulocytes count, MCV)	X				X	X	X	X	X	X				X	X	X
Coagulation (PT, INR)	X				X	X	X	X	X	X				X	X	X
Labs- Urinary Pregnancy tests	X					X	X	X	X	X				X	X	X
Labs – Serology HIV, HBs and HCV serology	X															
Labs – Biochemistry HbA1c, fasting plasma glucose, insulin, HOMA-IR, fructosamine, alkaline phosphatase, ALT, AST, GGT, CPK, total and conjugated bilirubin, ferritin, creatinine, eGFR, uric acid, BUN, total cholesterol, HDL-C, LDL-C, triglycerides, albumin, lipase, amylase, electrolytes (sodium, potassium, chloride, calcium), MELD	X			X ¹	X	X	X	X	X	X				X	X	X
Inflammatory markers hsCRP, fibrinogen, haptoglobin, resistin, TNF- α , TGF- β , IL-6, PAI-1	X				X			X						X	X	X

	Screening period				Treatment period											
Visit	SV	S V2	SV3	S V 4	V 1	V 2	V 3	V4	V5	V6	V7	V8	V9	V10	EOS	ET
Day	-42	- 14	-11	-7	1	29	57	85	113	141	155	158	162	169	+28 days	
Biomarkers of fibrosis ELF Score, PIIINP, Hyaluronic acid, CK18, TIMP-1, YKL-40, Alpha 2 macroglobulin,, ,miRNA, ProC3, ProC6, FGF19, FGF21	X				X			X						X	X	X
NAFLD Fibrosis Score (NAS) & FIB-4					X			X						X		X
Labs – Urinalysis dipstick Specific gravity, pH, protein, glucose, ketones, bilirubin, urobilinogen, blood, nitrite, leukocytes	X				X	X	X	X	X	X				X	X	X
Safety markers Serum Cystatin C, troponin T, NT proBNP Urinary albumin, urinary creatinine, urinary ACR	X				X	X	X	X	X	X				X	X	X
Labs -- FSR		X	X	X	X						X	X	X	X		
Sampling for additional parameters	X				X			X		X				X	X	X

6.8.4. Electrocardiogram

Standard 12-lead electrocardiogram (ECG) assessments will be performed. The Investigator will review the ECGs for any clinically significant abnormalities to ensure subject safety.

Abnormal ECG findings that are considered clinically significant by the Investigator and meet the definition of an AE should be reported and recorded in the AE eCRF page.

6.8.5. MRE

Liver stiffness will be assessed by MRE. It is recommended that each subject's radiological assessment is performed using the same procedure for each study visit. Exploratory measures for MRI/MRE sequence development will be maintained for future analysis.

6.8.6. Fibroscan

Liver stiffness will be assessed by FibroScan®. It is required that each subject's FibroScan® assessments be done with the same type of probe at each study visit.

6.8.7. Medical History

Medical history including details regarding illnesses and allergies, date(s) of onset, and whether condition(s) is currently ongoing, and medication history, including nicotine and alcohol use, will be collected on all subjects during screening.

6.8.8. Physical Examination

A complete physical examination should include source documentation of general appearance, and the following body systems: head, neck, and thyroid; eyes, ears, nose, throat, mouth, and tongue; chest (excluding breasts); respiratory; cardiovascular; lymph nodes; abdomen; skin, hair, nails; musculoskeletal and neurological.

The patient's weight will be measured under the same conditions at each visit where the procedure is required. Where possible, the scale for weight must be the same for a given patient throughout the visits.

6.8.9. Vital Signs

Blood pressure (mmHg) and pulse rate (beats per minute) will be measured at each visit using automated blood pressure equipment.

Important points for clinical blood pressure measurement

- The patient should be seated comfortably with the back supported and the upper arm bare without constrictive clothing. The legs should not be crossed.
- The arm should be supported at heart level, and the bladder of the cuff should encircle at least 80% of the arm circumference.

- Neither the patient nor the observer should talk during the measurement.

Systolic BP and diastolic BP will be measured after 5 minutes rest in the seating. Where possible, the blood pressure equipment should be the same for a given patient throughout the visits.

6.8.10. Pregnancy Testing

Urinary pregnancy tests will be done on WOCBP.

7. Adverse Events and Toxicity Management

7.1. Definitions of Adverse Events, Serious Adverse Events and Unexpected Events

7.1.1. Adverse Events

An adverse event (AE) is any untoward medical occurrence in a clinical study subject administered a medicinal product, which does not necessarily have a causal relationship with the treatment. An AE can therefore be any unfavorable and/or unintended sign, symptom, or disease temporally associated with the use of a medicinal product, whether or not considered related to the medicinal product. AEs may also include pre-or post-treatment complications that occur as a result of protocol specified procedures, overdose, drug abuse/misuse reports, or occupational exposure. Preexisting events that increase in severity or change in nature during or as a consequence of participation in the clinical study will also be considered AEs.

An AE does not include the following:

- Medical or surgical procedures such as surgery, endoscopy, tooth extraction, and transfusion. The condition that led to the procedure may be an adverse event and must be reported
- Pre-existing diseases, conditions, or laboratory abnormalities present or detected before the Screening visit that do not worsen
- Situations where an untoward medical occurrence has not occurred (eg., hospitalization for elective surgery, social and/or convenience admissions)
- Overdose without clinical sequelae.

- Any medical condition or clinically significant laboratory abnormality with an onset date before the consent form is signed and not related to a protocol-associated procedure is not an AE. It is considered to be pre-existing and should be documented on the medical history eCRF.

7.1.2. Clinical Laboratory Abnormalities and Other Abnormal Assessments as Adverse Events or Serious Adverse Events

Laboratory abnormalities without clinical significance are not recorded as AEs or SAEs. However, laboratory abnormalities (eg, clinical chemistry, hematology, and urinalysis) that require medical or surgical intervention or lead to study drug interruption, modification, or discontinuation must be recorded as an AE, as well as an SAE, if applicable. In addition, laboratory or other abnormal assessments (eg, electrocardiogram, x-rays, vital signs) that are associated with signs and/or symptoms must be recorded as an AE or SAE if they meet the definition of an AE or SAE as described above. If the laboratory abnormality is part of a syndrome, record the syndrome or diagnosis (eg, anemia), not the laboratory result (ie, decreased hemoglobin).

7.1.3. Serious Adverse Events

A serious adverse event (SAE) is defined as an event that, at any dose, results in the following:

- Death
- Life-threatening (Note: The term “life-threatening” in the definition of “serious” refers to an event in which the subject was at risk of death at the time of the event; it does not refer to an event that hypothetically might have caused death if it were more severe.)
- In-patient hospitalization or prolongation of existing hospitalization
- Persistent or significant disability/incapacity
- A congenital anomaly/birth defect
- A medically important event or reaction: such events may not be immediately life-threatening or result in death or hospitalization but may jeopardize the subject or may require intervention to prevent one of the

other outcomes constituting SAEs. Medical and scientific judgment must be exercised to determine whether such an event is a reportable under expedited reporting rules. Examples of medically important events include intensive treatment in an emergency room or at home for allergic bronchospasm; blood dyscrasias or convulsions that do not result in hospitalization; and development of drug dependency or drug abuse. For the avoidance of doubt, infections resulting from contaminated medicinal product will be considered a medically important event and subject to expedited reporting requirements.

7.1.4. Unexpected adverse event

Expectedness is assessed by the Sponsor-Investigator. An unexpected AE is defined as an event that has a nature of severity or specificity that is not consistent with the applicable Package Insert or that is symptomatically and pathophysiologically related to a known toxicity but differs because of a greater severity or specificity.

“Unexpected” refers to an event that has not been previously observed and reported rather than an event that has not been anticipated based on the properties of the drug.

7.2. Assessment of Adverse Events & Serious Adverse Events

The Investigator will establish whether or not any AE have occurred at each visit from the date of consent. The patient will be questioned in a general manner to determine specific symptoms without offering the patient any suggestion. The investigator or qualified sub-investigator is responsible for assessing AEs and SAEs for causality and severity, and for final review and confirmation of accuracy of event information and assessments.

7.2.1. Intensity assessment

The intensity of the AE will be graded as follows:

- Mild: Awareness of signs or symptoms, but easily tolerated and are of minor irritant type causing no loss of time from normal activities.

Symptoms do not require therapy or a medical evaluation; signs and symptoms are transient.

- Moderate: Events introduce a low level of inconvenience or concern to the participant and may interfere with daily activities, but are usually improved by simple therapeutic measures; moderate experiences may cause some interference with functioning.
- Severe: Events interrupt the participant's normal daily activities and generally require systemic drug therapy or other treatment; they are usually incapacitating.

7.2.2. Relation to the study treatment

The Investigator will make a clinical and scientific judgment regarding whether or not the AE was related to study treatment. The Investigator will evaluate any changes in laboratory values, make a determination as to whether or not the change is clinically important, and whether or not the changes were related to study drug. However, even if the Investigator feels there is no relationship to the study drug, the AE or clinically significant laboratory abnormality must be recorded in the eCRF.

The Investigator will record the relation to the study treatment according to the following causality terms:

- Related: the AE follows a reasonable temporal sequence from the time of drug administration and it cannot be explained by the patient's clinical state or the study procedures/conditions. The AE abates upon discontinuation of the study drug and reappears when the study drug is introduced.
- Possibly related: the AE follows a reasonable temporal sequence from the time of drug administration, but could have been produced by the patient's clinical state or the study procedures/conditions.

- Unlikely related: the temporal association between the AE and the study drug is such that the study drug is not likely to have any reasonable association with the AE. The relationship is not likely because of other plausible explanations.
- Not related: the AE must definitely be caused by the patient's clinical state or the study procedure/conditions. A reasonable explanation must be given, e.g., no investigational product taken, preplanned elective medical intervention, or incompatible temporal relationship.
- Not assessable: the report suggesting an adverse reaction cannot be judged because information is insufficient or contradictory and data cannot be supplemented or verified.

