6.6.1. Pre-specified Patient Discontinuation rules

If a patient experiences a Grade IV Common Terminology Criteria for Adverse Event (CTCAE) or meets liver injury criteria as listed in section 6.6.3., the study drug should be interrupted. After causality assessment by the DSMB, if the AE or lab abnormality is considered unrelated to study drug, and the event has resolved or returned to baseline, then the study drug may be re-

started. If the event reoccurs after restart of study drug, then the study drug will be permanently discontinued.

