6.6.3. Dose Adjustment

Enrolled subjects who experience treatment emergent adverse events should be monitored closely and may have the NTZ dose adjusted at the Principal Investigator's discretion.

Enrolled subjects who experience a possible treatment emergent adverse event will be assessed for symptoms and further biochemical assessments as follows:

- GI Adverse Events: the subject will be assessed for abdominal pain, loss of appetite, nausea and vomiting. Blood will be collected for amylase and lipase assessment to rule out pancreatitis.
- Kidney Function Adverse Events: the subject will have blood samples collected for eGFR to rule out kidney dysfunction.
- Musculoskeletal Adverse Events: the subject will be assessed for fatigue, muscle aches and pain. Blood samples will be collected for Creatine Kinase.

The following procedure will be followed for dose adjustments:

1. Patients will be asked to hold drug for 3 days
2. After the 3-day drug hold, patients will be reassessed for adverse event symptoms.
 - If the AE symptoms have resolved following 3 days of drug hold, the patient will discontinue NTZ dosing permanently and will be followed per the schedule of assessments.

If the AE symptoms have not resolved following 3 days of drug hold, the patient will be restarted on a reduced dose of 500 mg NTZ, once a day for 7 days. Patients will be evaluated for treatment emergent adverse events and consideration for resuming the dosage of 500mg NTZ twice a day. PI may determine that the patient should remain at the 500 mg NTZ once a day dose following 7 days of reduced dose. In such scenarios, the patient will be monitored and consideration for resuming the dosage of 500 mg NTZ twice daily will be evaluated at each subsequent visit.

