3.5 Safety Assessments

3.5.1 Adverse Events

All AEs regardless of seriousness or relationship to study drug, including those occurring during the Screening Period, are to be recorded on the corresponding page(s) of the CRF and in the patient's medical record from the informed consent form signature until study end for each patient. All AEs will be coded to system organ class and preferred term using Medical Dictionary for Regulatory Activities (MedDRA) version 21.0.

TEAEs are defined as AEs that worsen in severity or relationship to study drug or commence on or after the time of start of first study drug administration. This may include AEs that start during follow-up after the last dose of study drug.

Study drug related AEs are defined as AEs that are possibly related or related.

An overview of AEs based on the Safety Analysis Set will be provided including counts and percentages of subjects with the following:

- Any TEAEs (overall and by maximum severity)
- Any study drug related TEAEs (overall and by maximum severity)
- Any SAEs
- Any study drug related SAEs
- Any deaths due to AEs
- Any AEs leading to withdrawal from study or study drug
- Any study drug related AEs leading to withdrawal from study or study drug

Counts and percentages of subjects will also be presented by system organ class and preferred term for TEAEs and study drug related TEAEs. In addition, summaries will be provided by system organ class, preferred term, and maximum severity.

Listings will be presented specifically for SAEs and TEAEs leading to withdrawal from study or study drug.

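### Read literally, the causality terms in Protocol 7.2.2 leave no drug-related category for an AE with plausible timing, no other explanation and no observed re-exposure

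*Protocol*

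**What the plan says.** Protocol 7.2.2 gives the investigator five causality terms.

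- *Related* needs plausible timing, and that "it cannot be explained by the patient's clinical state or the study procedures/conditions". A further sentence follows without any qualifier such as 'where known': "The AE abates upon discontinuation of the study drug and reappears when the study drug is introduced".
- *Possibly related* also needs plausible timing, "but could have been produced by the patient's clinical state or the study procedures/conditions".
- *Unlikely related* rests on rival explanations: "The relationship is not likely because of other plausible explanations".
- *Not related* requires a definite other cause.
- *Not assessable* is for reports with insufficient or contradictory information.

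The analysis rule is in SAP 3.5.1: "Study drug related AEs are defined as AEs that are possibly related or related".

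Three protocol sections decide whether a patient is re-exposed after an AE.

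- 6.6.3 (three-day hold): "If the AE symptoms have resolved following 3 days of drug hold, the patient will discontinue NTZ dosing permanently". Dosing restarts, at a reduced dose, only when the symptoms have not resolved.
- 6.6.1 (Grade IV and liver-injury events): restart is allowed "if the AE or lab abnormality is considered unrelated to study drug" and the event has resolved or returned to baseline. The section also provides for an event that recurs after restart.
- 6.6.4 (liver monitoring): the DSMB may allow restart if it judges the event not related to study drug.

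**The concern.** *Related* depends on seeing the event stop off drug and come back on drug. *Possibly related* depends on there being another candidate cause. An event with good timing and no rival explanation, in a patient who is never re-exposed, satisfies neither. It does not fit *Unlikely related* or *Not related* either, because both rest on another cause. *Not assessable* does not describe it, and the SAP would not count it under that term anyway.

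The result is an inversion: adding a rival explanation moves the event into the drug-related count, and removing it takes the event out.

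This matters because safety and tolerability is the primary endpoint and SAP 2.2.2 confirms a single open-label group. With no control rate to set against the observed one, the drug-related summaries depend on the investigator's causality term.

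**Working it through.** The plan gives no figure on this point, and the sample size rests on clinical assessment, so there is no calculation to reproduce. The check sets the definitions against each route an AE can take.

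**Step 1. Rules applied, with plausible timing throughout.**

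- *Related* = no other explanation AND abates off drug AND reappears on drug (7.2.2).
- *Possibly related* = another possible cause (7.2.2).
- Counted = *Related* OR *Possibly related* (SAP 3.5.1).

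**Step 2. Routes.**

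| Route | Abatement seen | Reappearance seen | No other cause: counted? | Other possible cause: counted? |
|---|---|---|---|---|
| (a) Dose not changed | no | no | no | yes, *Possibly* |
| (b) 6.6.3 hold, AE resolves, permanent stop | yes | no | no | yes, *Possibly* |
| (c) 6.6.3 hold, AE does not resolve, restart | no | not applicable | no | yes, *Possibly* |
| (d) 6.6.1/6.6.4 interruption, judged related, no restart | yes, if it resolves | no | no | yes, *Possibly* |
| (e) 6.6.1/6.6.4 interruption, judged unrelated, restart, AE recurs | yes | yes | yes, *Related* | yes, *Possibly* |
| (f) Interruption for another reason (5.5, 6.7), AE abates, then returns on resumption | yes | yes | yes, *Related* | yes, *Possibly* |

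With no other cause, routes (a) to (d) are not counted. With another possible cause, all six are. *Related* can be reached only through (e), which starts from a judgment that the event was unrelated, or (f), where dosing stopped for some other reason.

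**Step 3. Which outputs use these terms.** From SAP 3.5.1: drug-related TEAEs (overall, by maximum severity, and by system organ class and preferred term), drug-related SAEs, and drug-related AEs leading to withdrawal. From Protocol 8.5.1: the tabulation by causality. All-cause TEAEs, SAEs, deaths and withdrawals, and the laboratory, vital-sign and ECG summaries, do not use them.

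**Step 4. Size, by illustration only.** Take n = 20 (Protocol 4.1) and assume all 20 are dosed. One patient is 1/20 = 5 percentage points. The documents do not say how many patients would fall in the gap, so the counts x below are assumptions, and each patient is taken to have no other AE counted as drug related. Exact 95% Clopper-Pearson limits are the 0.025 quantile of Beta(x, n − x + 1) and the 0.975 quantile of Beta(x + 1, n − x); for x = 0 the lower limit is 0 and the upper is 1 − 0.025^(1/20) = 16.8%.

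| Patients in the gap (assumed) | Literal reading | If counted |
|---|---|---|
| 1 | 0/20: 0% (0 to 16.8%) | 1/20: 5% (0.1 to 24.9%) |
| 2 | 0/20: 0% (0 to 16.8%) | 2/20: 10% (1.2 to 31.7%) |
| 3 | 0/20: 0% (0 to 16.8%) | 3/20: 15% (3.2 to 37.9%) |
| 5 | 0/20: 0% (0 to 16.8%) | 5/20: 25% (8.7 to 49.1%) |

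The 0/20 column further assumes that no other patient has a counted event.

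**The case against.** The strongest reply is that the gap exists only for a strictly literal reader. Section 7.2.2 opens by asking for clinical and scientific judgment, and 7.3.1 asks whether there is a reasonable possibility that the drug caused the AE. An investigator who believes the drug was responsible would probably record *Possibly related*, and the SAP pools that with *Related*. Many of the expected events are non-specific (gastrointestinal symptoms, headache, fatigue), so another cause can seldom be excluded over 24 weeks. The all-cause results and individual AE listings remain, and the DSMB makes its own causality assessment when deciding on pauses and restarts.

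Most of this stands, and it limits the point. It does not remove it: the pooled row is protected only if investigators depart from the written definition, and the split between the two terms in 8.5.1 then loses its meaning.

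A reader might go further and infer three things that the documents do not support.

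- That the hold and restart rules rule out *Related* altogether. They do not: 6.6.1 foresees recurrence after restart, 6.7 allows dosing to resume after intercurrent illness, and 5.5 provides for interruptions from any cause.
- That every AE managed without a hold drops out of the drug-related row. Such an AE usually cannot be *Related*, but it is still counted as *Possibly related* whenever another cause is possible.
- That chromaturia, listed in 1.2.2 among the most common reactions, is a sure example. Nothing in the documents says it has no disease explanation in patients with NASH and fibrosis.

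**Conclusion.** The definitions do leave a gap. Applied as written, they omit from the drug-related count an AE with plausible timing, no alternative explanation and no observed re-exposure, while counting a more ambiguous one. Re-exposure is unlikely for the clearest reactions, because 6.6.3 ends dosing when the AE resolves on hold and 6.6.1 and 6.6.4 allow restart only after a judgment of unrelated. It remains possible by the two side routes.

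The consequence is limited to the drug-related summaries and to the *Related* versus *Possibly related* split. The size is unknown: up to 5 percentage points per affected patient if 20 are dosed, and nothing in the pooled row if investigators use *Possibly related* more broadly than it is defined. The conclusion rests on reading the abatement and reappearance sentence as a requirement, which is how it is phrased. How the eCRF handles these terms cannot be seen from the documents.

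**What to change.** In Protocol 7.2.2, define *Related* as plausible timing and not explained by the patient's clinical state or by study procedures or conditions. State that abatement off drug and recurrence on re-exposure are supporting evidence where they were observed, not conditions. Leave the other four terms and the SAP 3.5.1 definition unchanged. For AEs with plausible timing, *Related* and *Possibly related* are then separated by a single question, whether another cause is possible, and routes (a) to (d) with no other cause become countable.

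No hold, stopping or restart rule needs to change for this, and no view is taken here on those rules.

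The cost is one sentence, carried into any eCRF completion guidance that repeats the definitions. No new data are needed. The downside is that the reported drug-related rate may be slightly less favourable.
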